#### *Other Non-Hematologic Toxicity*

For other grade 3 non-hematologic toxicity, lenalidomide should be held until toxicity resolves to  $\leq$  grade 2, then the study drug should be resumed at the next lower dose level. Subjects are not allowed to continue study treatment if toxicity persists more than 8 weeks.

For patients who develop grade  $\leq 2$  non-hematologic toxicity, an attempt will be made to maintain the patient at that dose level. If the patient cannot tolerate this dose level, the treating physician should decrease the dose to the next lower dose level.

For other grade 4 non-hematologic toxicity, discontinue study drug and contact the Study Chair or Co-Chair.

In the event of any grade 1 or 2 toxicity that the patient finds intolerable, the study drug may be held until the toxicity resolves and the study drug resumed at the next lower dose level. Alternatively, the study drug may be continued at the next lower dose level without cessation of study drug. However, study drug should be held for the occurrence of a rash consistent with evolving Stevens-Johnson syndrome or toxic epidermal necrolysis (bullous, blistering that is purpuric in nature) until appropriate evaluation is made. Study drug may be held for up to 8 weeks. Contact the Study Chair or Co-Chair for consultation.

## 5.2 Concomitant Medications

No investigational or commercial agents or therapies other than those described below may be administered with the intent to treat the patient's malignancy.

Participants who receive radiation therapy or chemotherapy after transplantation are considered to have treatment failure, unless the radiation was pre-planned consolidation and that decision was made before transplantation.

Any other treatments (including drugs, biological products, and blood products) the patient is receiving at the time of screening or has received within one to four weeks prior to registration and during therapy should be recorded on the concomitant medications page of the case report forms (CRFs). Use of colony stimulating factors (G-CSF or GM-CSF) and Erythropoietin are prohibited during the study. Subjects who need colony stimulating factors or erythropoietin should be taken off from the study.

All concomitant medications and supportive therapy received during study treatment must be recorded.

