**Adverse Events**

Most frequently reported adverse events reported during clinical studies with lenalidomide in oncologic and non-oncologic indications, regardless of presumed relationship to study medication include: anemia, neutropenia, thrombocytopenia and pancytopenia, abdominal pain, nausea, vomiting and diarrhea, dehydration, rash,

itching, infections, sepsis, pneumonia, Urinary Tract Infections (UTI) , Upper respiratory infection, atrial fibrillation, congestive heart failure, myocardial infarction, chest pain, weakness, hypotension, hypercalcemia, hyperglycemia, back pain, bone pain, generalized pain, dizziness, mental status changes, syncope, renal failure, dyspnea, pleural effusion, pulmonary embolism, deep vein thrombosis, Cerebrovascular attacks (CVA), convulsions, dizziness, spinal cord compression, syncope, disease progression, death not specified and fractures.

Lenalidomide has been studied in healthy volunteers and in patients with cancer of the blood and other organs of the body as well as in patients with other diseases. As with any other experimental treatment there may be side effects or risks associated with lenalidomide, some of which are not yet known.

The following is a list of the most medically significant or most common side effects reported in completed and ongoing studies considered to be related to lenalidomide. In some cases, side effects can be serious, long-lasting, may never go away, or can cause death.

Common (between a 1-10% chance that this will happen):

Anemia; Decrease in cells that help your blood clot; Low white blood cells with or without fever; Pneumonia or other infections; Fever; Abnormal heart beats; Shortness of breath; Blood clots in lower extremities, lungs, heart, brain or other organs; Abnormal kidney function; Diarrhea with or without bleeding; Loss of fluid; Other cancers; Pain including muscles, joints and non-heart pain; Altered sense of taste.

Uncommon (between a 0.1-1% chance that this will happen):

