## 5. TREATMENT PLAN

Treatment will be administered on an outpatient basis. Lenalidomide 2.5 mg, 5 mg, 10 mg, 15 mg and 25 mg capsules are to be taken orally (PO). In Phase I, the starting dose of Lenalidomide is 10 mg taken PO daily for 3 consecutive weeks (Days 1-21) following one week off therapy (Days 22-28). One cycle is 4 weeks (Figure 1).

**Figure 1:** Phase 1 and Phase 2 Lenalidomide Dosing Schema

In phase 1, it is anticipated that 6 - 18 evaluable patients will be treated. Three to six patients will be treated at each dose level of three dose levels of Lenalidomide (10 mg, 15 mg, 25 mg) daily doses (Table 1). The initial dose is 10 mg. Patients will receive repeated cycles of Lenalidomide until disease progression or unacceptable toxicity. If no Lenalidomide related Dose Limited Toxicity (DLT) is seen in three patients at a dose level during first cycle (by day 28), the escalation to the next dose level is allowed. Each cohort will be monitored for a DLT during the first cycle before deciding to escalate the dose for the next cohort.

**Table 1:** Phase 1 Dose ranging

Dose Level	Daily Dose (once a day)	Number of Patients	Escalation Rule *
-1	5 mg	3 – 6	If 0/3 DLT or 1/3 DLT add 3 patients
1 (Starting Dose)	10 mg	3 – 6	If 0/3 DLT escalate 1/3 DLT add 3 patients
2	15 mg	3 – 6	If 0/3 DLT escalate 1/3 DLT add 3 patients
3	25 mg	3 – 6	If 0/3 DLT or 1/3 DLT add 3 patients

\* Dose escalation rules are described in details in Table 2.

Dose escalation determination is summarized in Table 2. If one DLT occurs at a dose level, up to 3 additional patients will be added to that cohort and if one or more of this group suffers DLT, then dose escalation is stopped, and this dose is declared the Maximally Tolerated Dose (MTD). Three additional patients will be entered at the next lower dose level if only three patients were treated previously at that dose.

**Table 2:** Determination of Lenalidomide Capsules Maximum Tolerated Dose (MTD)

Number of Patients with DLT at Given Dose Level	Dose Escalation Rule
0 out of 3	Enter three patients at the next dose level
≥ 2	Dose escalation will be stopped. This dose level will be declared MTD. Three additional patients will be recruited at the next lower dose level if only three patients were treated previously at that dose.

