1 out of 3	Recruit at least three more patients at this dose level. 
 
• If none of these patients experience with DLT, proceed to the next higher dose level
 
• If one or more of this group suffer DLT, then dose escalation is stopped and this dose is declared MTD. Three additional patients will be entered at the next lower dose level if only three patients were treated previously at that dose.
 

≤ 1 out of 6 at highest dose level below the MTD	This will be the recommended Phase 2 dose. At least six patients must be recruited at the recommended Phase 2 dose.

If no DLT is observed at the final 25 mg dose level in the first three patients, three additional patients at the 25 mg dose level will be recruited. In Phase 1, in order to declare Therapeutic Dose Level (TDL), a minimum of six patients must be recruited at that dose level. Therapeutic

Dose Level (TDL) is defined as the dose level where DLT occurred in less or equal to one out of six patients below the Maximally Tolerated Dose level. TDL will be the recommended dose for Phase 2.

If a DLT is observed in two or more patients at the first dose level (10 mg), then dose level -1 (5 mg) will be tested with three patients first. Three additional patients will be enrolled at the 5 mg dose, if one or less DLT is observed. If one or more of this group suffers DLT, then the study is stopped and lenalidomide maintenance for elderly AML patients post autologous transplant is not deemed feasible (same as if  $\geq 2$  had a DLT to initial cohort of 5 mg).

Decisions about DLTs, expansion of a cohort to six subjects, escalation to the next dose level, or reduction to the next lower level will be made by Principle Investigator.

In Phase 1, subjects will continue study drug, lenalidomide until disease progression or unacceptable toxicity. Reported adverse events and potential risks for lenalidomide are described in Section 2.5. Dose modifications are described in Sections 5.1 and in Table 3. Subjects who are withdrawn without a DLT before completing Cycle 1 will not be used to evaluate the MTD or TDL, but will be included in the overall safety analysis.

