### **5.1 Dose modifications**

At Phase 1, subjects who develop any DLT during cycle 1 will be taken off the study. During cycle 2 and onward, dose reductions are allowed. Dose reduction rules are the same for subjects enrolled in Phase 2 (Table 3). Reduced doses will not be re-escalated for any subject during the study. Subjects may not continue Lenalidomide after the third dose reduction or beyond dose of 2.5 mg.

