**Table 3: Lenalidomide Capsules Dose Modifications**

Original Daily Dose (mg)	First Dose Reduction (mg)	Second Dose Reduction* (mg)	Third Dose Reduction* (mg)
5	2.5	Discontinue	N/A
10	5	2.5	Discontinue
15	10	5	2.5
25	15	10	5

\* Subjects may not continue Lenalidomide after third dose reduction or beyond dose of 2.5 mg.

A non-hematologic DLT is defined as a National Cancer Institute (NCI)-Common Terminology Criteria for Adverse Events (CTCAE) Version 4 (Oct/09) Grade 3 or 4 adverse events (AE) considered related to the study drug. Grade 3 anorexia and Grade 3 fatigue are excluded since it is very common to develop anorexia and fatigue during any chemotherapy.

A hematologic DLT is defined as a grade 4 hematologic toxicity complicated by infection, severe hemorrhage, or marrow aplasia persisting greater than 2 weeks considered related to the study drug.

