## 5.3 Supportive Care

Prophylactic aspirin or low molecular weight heparin are to be given to all patients receiving lenalidomide (as DVT prophylaxis) unless contraindicated. Prophylactic blood product support is discouraged however blood product transfusions are allowed for symptomatic patients who have clinically significant anemia or thrombocytopenia.

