## 5.4 Removal from the study

Subjects may take the study drug indefinitely unless removed or withdrawn from the study. The following are criteria for removal from the study:

- Disease progression. Disease progression is defined as a bone marrow biopsy showing >5% myeloblasts.
- Intercurrent illness that prevents further administration of treatment,
- Occurrence of any adverse event (AE), intercurrent illness or abnormality in laboratory assessment results which, in the opinion of the investigator, warrants the subject's permanent withdrawal from the trial
- Treatment with a prohibited concomitant medication other than the use of appropriate medications for the treatment of adverse events under direction of the

investigator (Protocol section 5.2)

- Participant becomes pregnant
- Participant is lost to follow-up
- Patient decides to withdraw from the study, or
- General or specific changes in the patient's condition render the patient unacceptable for further treatment in the judgment of the investigator.

If a participant discontinues the trial prematurely, the reason given must be fully evaluated and recorded appropriately in source documents and the CRF. If the subject is being withdrawn because of an adverse event (AE), that AE should be indicated as the reason for withdrawal.

All participants have the right to withdraw at any time during treatment without prejudice. The investigator can discontinue a subject's participation in the trial at any time if medically necessary. The Principal Investigator should be notified promptly when a subject is withdrawn.

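### Phase 1: a cycle 1 removal because lenalidomide-related cytopenia needs a growth factor adds nothing to the formal 3+3 tally unless it already meets the complicated grade 4 DLT definition

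*Combined protocol and SAP*

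**What the plan says.** Four rules in the combined protocol and SAP meet here.

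- **Removal.** Section 5.2 prohibits G-CSF, GM-CSF and erythropoietin on study: "Subjects who need colony stimulating factors or erythropoietin should be taken off from the study". No phase or cycle limit is given.
- **DLT definition.** Under Table 3 in Section 5.1: "A hematologic DLT is defined as a grade 4 hematologic toxicity complicated by infection, severe hemorrhage, or marrow aplasia persisting greater than 2 weeks", and it must be considered related to study drug. Neither need for growth factor nor permanent discontinuation is a criterion.
- **Evaluability.** Section 5: "Subjects who are withdrawn without a DLT before completing Cycle 1 will not be used to evaluate the MTD or TDL". They stay in the overall safety analysis. The rule does not separate drug-related from unrelated withdrawal.
- **Consequence of a DLT.** Section 5.1: "subjects who develop any DLT during cycle 1 will be taken off the study".

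Three further texts limit or blur the point. Section 5.3 says "blood product transfusions are allowed for symptomatic patients who have clinically significant anemia or thrombocytopenia". Section 5.4 lists as a removal criterion "Treatment with a prohibited concomitant medication other than the use of appropriate medications for the treatment of adverse events under direction of the" investigator, citing Section 5.2; it does not say whether growth factors fall under the exemption. On numbers, Section 5 says only: "In phase 1, it is anticipated that 6 - 18 evaluable patients will be treated".

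**The concern.** Defining the MTD and TDL is objective 1.2.1, and the 3+3 count fixes the dose for the 30 Phase 2 patients, who are aged 60 to 80 and treated until progression or unacceptable toxicity. Myelosuppression is the toxicity the protocol expects of lenalidomide (Table 5), and patients may enter with an absolute neutrophil count of 1,000 (3.1.7).

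Two patients can therefore both lose treatment in cycle 1 through related marrow toxicity, with only one counted. The first has a complicated grade 4 event, which is a DLT. The second has a grade 4 neutropenia that the clinician judges to need G-CSF before any complication. That patient must leave under 5.2, has no DLT, and drops out of the tally. The hematologic hold-and-reduce rules in 5.1.1 apply in Phase 1 only after cycle 1, so no written dose-modification route for low counts competes with removal. Section 5.1 is stricter elsewhere: a related grade 3 non-hematologic event is a DLT without any complication, apart from fatigue and anorexia.

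**Working it through.** **The plan's own figure.** Following every path through Tables 1 and 2 (10, 15 and 25 mg, with 5 mg as level -1, and filling the recommended level to six) gives totals of 6, 9, 12, 15 or 18 evaluable patients. The stated range of 6 to 18 reproduces.

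**Inputs.**
- d = rate of protocol-defined DLT in cycle 1. Assumed 10% or 20%.
- g = rate of cycle 1 removal for related growth-factor need without a DLT. Assumed 1%, 5% or 10%.

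The documents give neither. The nearest text is the side-effect list in Section 2.5, which puts related anemia and low white cells under "Common (between a 1-10% chance that this will happen". That pools other populations and is not a rate of growth-factor need in cycle 1, so it is only a loose guide to the range.

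**Formula.** A dose is passed with 0 of 3 DLTs, or with 1 of 3 followed by 0 of 3. With p the per-patient probability of a counted event and q = 1 − p:

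P(escalate) = q³ + 3pq² × q³

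This applies to 10 mg and 15 mg, where a higher level exists.

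**Three treatments of the removed patient.**
- Counted as a DLT: p = d + g
- Left out and the place refilled: p = d/(1 − g)
- Kept as a non-DLT: p = d

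Refilling is inferred from the three-patient cohort rules and the word evaluable; the protocol does not state it.

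Example, d = 10% and g = 5%. Counted: p = 0.15, so 0.85³ + 3(0.15)(0.85⁵) = 0.814. Left out: p = 0.10/0.95 = 0.105, giving 0.897. Kept: p = 0.10, giving 0.906.

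| d | g | Counted | Left out | Kept as non-DLT | Left out − counted (points) | Kept − left out (points) |
|---|---|---|---|---|---|---|
| 10% | 1% | 0.889 | 0.904 | 0.906 | 1.5 | 0.2 |
| 10% | 5% | 0.814 | 0.897 | 0.906 | 8.4 | 0.9 |
| 10% | 10% | 0.709 | 0.887 | 0.906 | 17.9 | 1.9 |
| 20% | 1% | 0.687 | 0.704 | 0.709 | 1.7 | 0.4 |
| 20% | 5% | 0.600 | 0.686 | 0.709 | 8.6 | 2.3 |
| 20% | 10% | 0.494 | 0.660 | 0.709 | 16.6 | 4.8 |

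**How often it would arise.** The chance of at least one such removal among the first three patients is 1 − (1 − g)³: 3%, 14% or 27% at g = 1%, 5% or 10%. In simulation (200,000 runs per setting), a dose is passed despite two or more treatment-ending events (DLT or removal) in about 1%, 6%, or 11 to 12% of cohorts. That count includes the excluded patients, so its denominator can exceed six and it should not be read against the 2-of-6 rule.

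**Aplasia window.** Days x to 28 number 29 − x. For more than 14 days by day 28, aplasia must begin by day 14 (29 − 14 = 15). Removal or growth factor may stop the criterion from being met or observed.

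**The case against.** The strongest reply is that this is a preference about the DLT threshold. The protocol appears to regard uncomplicated cytopenia as expected: Table 5 exempts grade 3 to 4 cytopenias from expedited reporting, with neutropenia and thrombocytopenia reported only beyond 15 days. Counting growth-factor need would also make a DLT depend partly on a prescribing decision. The second part stands, and a grade 4 requirement limits it. The first part stands only in part, because the plan itself makes this toxicity end treatment.

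The group is also small. Complicated grade 4 events already count; clinically significant anemia or thrombocytopenia with symptoms can be transfused on study; growth-factor- or transfusion-dependent patients are excluded (3.2.4). This stands.

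Safeguards exist: the safety analysis, adverse-event follow-up (6.4), monthly committee review of adverse events (11.1), and the principal investigator's decision on DLTs (Section 5). None is a written rule that makes the event count. If the 5.4 exemption did cover growth factors, the patient would stay as a non-DLT and the event would still not count.

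A reader might infer that the evaluability rule itself pushes the dose upward. It does not: leaving the patient out is 0.2 to 4.8 points more cautious than keeping the patient as a non-DLT. A reader might also infer that every treatment-ending withdrawal in cycle 1 should be a DLT. That would override the protocol's express exclusion of grade 3 fatigue and anorexia and would count withdrawals for intolerable grade 1 to 2 effects; nothing here supports it.

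**Conclusion.** The gap is real but narrow. Read together, Sections 5, 5.1 and 5.2 let a related cytopenia end treatment in cycle 1 without entering the 3+3 tally, unless it is already a complicated grade 4 event. To say the toxicity never counts at all would go too far: it is absent from the formal MTD and TDL evaluation only.

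Compared with counting the event, the plan raises the chance of escalating by about 2 points at 1% need, 8 to 9 at 5%, and 17 to 18 at 10%, per dose level. These figures rest on assumed rates, on refilling of the excluded place, and on every such removal being one that would count. If some removals are below grade 4, the fix below would have a smaller effect. At 1% the matter is minor; at 5% to 10% it could affect the Phase 2 dose. It is worth correcting because the correction is cheap.

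**What to change.** 1. **Section 5.1.** Add that a lenalidomide-related grade 4 hematologic toxicity in cycle 1 that requires growth factor, and so removal under 5.2, is a DLT. Add that anemia manageable by transfusion under 5.3 is not a need for erythropoietin, so that drug choice alone does not create a DLT.
2. **Section 5.** State that a cycle 1 withdrawal for lenalidomide-related hematologic toxicity is not treated as non-evaluable, and that the patient is followed to day 28 so that a later-qualifying DLT is counted. Leave the non-hematologic DLT definition and its fatigue and anorexia exclusions unchanged.
3. **Section 5.4.** State that the adverse-event exemption does not cover the growth factors prohibited in 5.2.

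**Cost.** Mostly wording. The safety follow-up in 6.4 already provides for unresolved adverse events, but observation to day 28 should be made explicit for these patients. Escalation becomes somewhat more cautious, so Phase 2 may run at a lower dose. Some dependence on the clinician's judgment that G-CSF is needed remains. A patient removed with toxicity below grade 4 would stay in the denominator as a non-DLT unless a DLT follows by day 28, which is marginally less cautious than dropping that patient (the last column of the table bounds this).

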## 5.3 Supportive Care

Prophylactic aspirin or low molecular weight heparin are to be given to all patients receiving lenalidomide (as DVT prophylaxis) unless contraindicated. Prophylactic blood product support is discouraged however blood product transfusions are allowed for symptomatic patients who have clinically significant anemia or thrombocytopenia.

## 5.4 Removal from the study

Subjects may take the study drug indefinitely unless removed or withdrawn from the study. The following are criteria for removal from the study:

- Disease progression. Disease progression is defined as a bone marrow biopsy showing >5% myeloblasts.
- Intercurrent illness that prevents further administration of treatment,
- Occurrence of any adverse event (AE), intercurrent illness or abnormality in laboratory assessment results which, in the opinion of the investigator, warrants the subject's permanent withdrawal from the trial
- Treatment with a prohibited concomitant medication other than the use of appropriate medications for the treatment of adverse events under direction of the

investigator (Protocol section 5.2)

- Participant becomes pregnant
- Participant is lost to follow-up
- Patient decides to withdraw from the study, or
- General or specific changes in the patient's condition render the patient unacceptable for further treatment in the judgment of the investigator.

If a participant discontinues the trial prematurely, the reason given must be fully evaluated and recorded appropriately in source documents and the CRF. If the subject is being withdrawn because of an adverse event (AE), that AE should be indicated as the reason for withdrawal.

All participants have the right to withdraw at any time during treatment without prejudice. The investigator can discontinue a subject's participation in the trial at any time if medically necessary. The Principal Investigator should be notified promptly when a subject is withdrawn.

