#### **3.2 Exclusion Criteria**

- 3.2.1. Patient received chemotherapy or radiotherapy within 2 weeks prior to entering the study or has not recovered from adverse events due to agents administered more than 4 weeks earlier.
- 3.2.2 Patient received another investigational agent after post autologous stem cell transplant.
- 3.2.3 Patient who will be receiving another investigational product during the study.

- 3.2.4 Patient who is growth factor or transfusion dependent.
- 3.2.5 Patient has CNS leukemia.
- 3.2.6 History of allergic reactions attributed to thalidomide or lenalidomide.
- 3.2.7 History of erythema nodosum, characterized by a desquamating rash while taking thalidomide or similar drugs.
- 3.2.8 Prior history of metastatic malignancy.
- 3.2.9 Uncontrolled illness including, but not limited to ongoing or active infection, unstable angina pectoris, cardiac arrhythmia, or psychiatric illness/social situations that would limit compliance with study requirements. Patients must not have suffered recent (< 6 months) myocardial infarction, unstable angina, uncontrolled hypertension, or difficult to control cardiac arrhythmias.
- 3.2.10 Evidence of uncontrolled Congestive Heart Failure (CHF).
- 3.2.11 Active Hepatitis B as defined by Hepatitis B surface antigen positivity, unless able to start dual anti-HepB therapy, or already on dual anti-HepB therapy
- 3.2.12 Patients who are positive for Hepatitis B core antibody, but negative for the hepatitis B surface antigen, should be on lamivudine 100 mg daily until at least 3 months post-transplant
- 3.2.13 Patient is positive for HIV or HTLV-1.
- 3.2.14 Women of childbearing potential (defined as a sexually mature woman who has not undergone a hysterectomy or who has had menses at any time in the preceding 24 consecutive months).
- 3.2.15 Men who did not agree not to father a child and who refused to use a latex condom during any sexual contact with women of childbearing potential while taking lenalidomide and for 4 weeks after therapy is stopped, even if they have undergone a successful vasectomy.

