### **Bone marrow biopsies**

Bone Marrow biopsy should be performed prior to or during Cycle 4 Week 1 visit, and should be repeated every four cycles during the first year, and every 6-8 cycles thereafter at the discretion of investigator, until disease progression.

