## **8 MEASUREMENT OF EFFECT**

### **8.1 Response Assessment**

For the purposes of this study, subjects' bone marrow aspirate and biopsies will be used at regular intervals to assess progression. Please see Section 6.2 for the schedule.

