### **8.2 Survival End Points**

#### **Progression-Free Survival**

Progression free survival (PFS) is defined as the duration of time from starting lenalidomide to time of progression.

**Progressive diseasea** is defined by the following:

- 5% myeloblasts on bone marrow aspirate and biopsy.

**Abbreviations:** CR, complete response; DFS, disease-free survival.

aAll relapse categories require two consecutive assessments made at anytime before classification as relapse or disease progression and/or the institution of any new therapy.

**Event-free survival (EFS):** The definition of an event is 1) disease progression or 2) death from any cause. EFS is the time from stem cell transplant until an event as defined above has occurred.

**TTP (Time to Progression):** This is the time from start of treatment to disease progression with deaths owing to causes other than progression not counted, but censored. This is a helpful method to assess the durability of treatment benefit.

**Overall survival (OS)** is defined as the time from transplant until death of any cause.

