## **Appendix D –Required Laboratory Parameters**

### **Complete Blood Count (CBC) with differential:**

White Blood Cells (WBC) count  
Red Blood Cells (RBC) count  
Hemoglobin  
Platelet count  
Neutrophil (%)  
Lymphocyte (%)  
Monocyte (%)  
Eosinophil (%)  
Basophil (%)  
Absolute Neutrophil count  
Absolute Lymphocyte count

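### Progression is defined by marrow myeloblasts alone, so leukaemia returning outside the marrow is not a progression event and relapse first seen in blood may be dated late

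*Combined protocol and SAP*

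**What the plan says.** Progression is described in three places, each time by the marrow only. Among the removal criteria, section 5.4 says: "Disease progression is defined as a bone marrow biopsy showing >5% myeloblasts". Section 8.1 says that "bone marrow aspirate and biopsies will be used at regular intervals to assess progression". Section 8.2 lists a single criterion for progressive disease, "5% myeloblasts on bone marrow aspirate and biopsy", with a footnote: "All relapse categories require two consecutive assessments made at anytime before classification as relapse or disease progression". The footnote speaks of relapse categories, but only one is listed.

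Section 6.2 sets a marrow at or before cycle 4 week 1, and says it "should be repeated every four cycles during the first year, and every 6-8 cycles thereafter at the discretion of investigator". Cycles last four weeks.

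Outside the marrow, three texts bear on the point:

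- **Section 3.2.5** excludes a patient at entry if "Patient has CNS leukemia". No on-study CNS event is defined.
- **Section 5.2** says: "Participants who receive radiation therapy or chemotherapy after transplantation are considered to have treatment failure", with an exception for radiotherapy planned before transplant. Sections 8.2 and 10.1 do not use that term.
- **Appendix D**, under "Complete Blood Count (CBC) with differential", lists neutrophils, lymphocytes, monocytes, eosinophils and basophils, with absolute neutrophil and lymphocyte counts. There is no blast entry. The appendix ends by requiring clinically significant laboratory results to be graded and entered on the adverse event page.

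Section 10.1 makes two-year relapse-free survival the aim of the study, with about 30 patients, and does not define relapse.

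**The concern.** AML can return in blood, the CNS or other tissue, and the protocol accepts leukaemia outside the marrow as disease when it screens for CNS involvement. Once the patient is on study, the same finding is not progression unless the marrow also crosses the threshold. A blood count is taken at every treatment visit, yet the plan neither asks for blasts to be reported nor lets them count.

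Both gaps act in one direction. A relapse that is not registered raises the relapse-free rate. A relapse that is registered late lengthens PFS and TTP, and raises the two-year rate if its date moves past two years. The trial has one arm and tests its rate against an assumed reference, so no randomised control is measured in the same way.

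**Working it through.** **1. The plan's own figures.** Inputs from section 10.1: n = 30, relapse 60% with and 90% without lenalidomide, so relapse-free survival 40% against 10%.

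- Standard error at 40%: √(0.40 × 0.60 / 30) = 8.94%, which agrees with the stated 9% or less.
- Power: the plan states over 80%, and gives no significance level. At an assumed one-sided 0.05, the exact binomial rule is success at 7 or more of 30 relapse-free, with false-positive chance 2.6% and power 98.3%. The stated power holds as a lower bound.

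**2. Which findings count under the text as written.**

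| Finding on study | Progression (5.4, 8.2) | Other handling |
|---|---|---|
| Marrow blasts over threshold | Yes | none needed |
| CNS or tissue leukaemia, marrow below threshold | No | Treatment failure under 5.2 if chemotherapy or radiotherapy is given; used by no endpoint |
| Blasts in blood, no marrow yet | No | Perhaps an adverse event page entry; no marrow required |
| Death | Not as progression | Event in EFS and OS |

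**3. Effect of unregistered relapses.** Expected relapses: 30 × 0.60 = 18. One missed relapse moves the rate by 1/30 = 3.3 points. Let f be the share of relapses that never meet the marrow criterion and are not otherwise counted. The documents give no value for f; 3% to 10% is assumed. The observed rate is the true rate + f × (1 − true rate).

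| f | Relapses lost of 18 | A true 40% reads as | A true 10% reads as | Chance of 7 or more of 30 at a true 10% |
|---|---|---|---|---|
| 0 | 0 | 40.0% | 10.0% | 2.6% |
| 3% | 0.54 | 41.8% | 12.7% | 7.8% |
| 5% | 0.90 | 43.0% | 14.5% | 13.4% |
| 10% | 1.80 | 46.0% | 19.0% | 34.0% |

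The upward shift at the planned rate is 1.8 to 6.0 points. The last column applies only if the 10% reference counts every relapse, which the documents do not say.

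**4. Effect of late dating.** Visits fall every 4 weeks from cycle 3. Planned marrows are 4 cycles (16 weeks) apart in year 1 and 6 to 8 cycles (24 to 32 weeks) apart later. A relapse visible in blood at the first visit after a clear marrow, but dated at the next planned one, is late by up to 16 − 4 = 12 weeks in year 1, and by up to 24 − 4 = 20 to 32 − 4 = 28 weeks afterwards.

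Counting from the start of treatment, with marrows at week 1 of cycles 4, 8 and 12, planned marrows fall on days 84, 196 and 308. They then fall on days 476, 644 and 812 (6-cycle gap) or 532 and 756 (8-cycle gap). The last before two years (day 730.5) is therefore day 644 or day 532. A relapse after that, dated only at the next planned marrow, falls beyond two years.

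As an upper bound, suppose every relapse were dated this way and the hazard were constant. A true 40% would then read as 0.40^(644/730.5) = 44.6% or 0.40^(532/730.5) = 51.3%. The real effect lies below this, by however many relapses lead to an earlier marrow.

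**The case against.** The strongest reply is that such patients are not invisible. Chemotherapy or radiotherapy for an extramedullary relapse is treatment failure under 5.2, death from any cause is an EFS event, and 5.4 lets the investigator withdraw a patient on several other grounds. All of this is true, and it limits the damage. But treatment failure enters no endpoint, an untreated relapse does not trigger it, and withdrawal is not a relapse event.

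A reader might infer three stronger things that the documents do not support:

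- **That a patient with CNS relapse counts as relapse-free at two years.** Relapse-free survival is undefined in section 10.1, so the patient's status there is undetermined. The inference holds only if relapse means progression as in 8.2.
- **That circulating blasts cannot be captured.** Appendix D lists the required parameters and does not bar others. Blasts could also reach the adverse event page as a clinically significant result. What is missing is a dedicated field and any role in the endpoint.
- **That blood relapse is always dated at the next planned marrow.** An unscheduled marrow is not barred, and 8.2 lets assessments be made at any time. The delays above are the latest dates the plan allows, not a rule it sets.

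It is also fair to say that the shift of 1.8 to 6 points rests on an assumed share and is smaller than the planned standard error of 9 points. A shift in one direction is not reduced by that comparison, however. Whether the 90% or over-95% reference shares the error cannot be judged, because its definition of relapse is not given.

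Lastly, a marrow threshold mirrors the entry definition of remission (under 5% myeloblasts, section 6.1), and an eligibility exclusion does not by itself make the endpoint contradictory. That stands. The point rests on what the endpoint fails to register, not on a contradiction with section 3.2.5.

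**Conclusion.** The point holds in this form. As written, leukaemia returning in the CNS or other tissue with marrow blasts below the threshold is not a progression event for PFS, TTP or EFS. It is not an event in the two-year rate either, if relapse there means progression as in 8.2. Relapse first seen in blood has no criterion and no required field, and no marrow is triggered by it, so its date depends on the investigator.

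The error raises the relapse-free rate by 3.3 points per missed relapse. It comes to 1.8 to 6 points if 3% to 10% of relapses are missed, at the planned 60% relapse and 30 patients. That share is an assumption. Late dating adds to this only for relapses moved past two years, by an amount the documents do not allow one to fix. The change should be made, since it bears on the endpoint that carries the study's aim and costs little.

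**What to change.** In section 8.2, give one definition of relapse and apply it to the two-year endpoint of 10.1, PFS, TTP and EFS. Relapse is any of:

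- marrow myeloblasts at the stated threshold;
- leukaemic blasts in peripheral blood, confirmed on a repeat CBC;
- documented CNS or other extramedullary leukaemia.

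Date the relapse at the first qualifying finding, once the two-assessment rule in the 8.2 footnote is met. State that treatment failure under 5.2, when the treatment is for leukaemia, counts as an event. Add blast percentage to the Appendix D differential and to the CRF.

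Sections 5.4 and 8.2 must be reconciled so that progression is described in one way. Whether and when treatment should stop is for the protocol team, and no removal rule is proposed here.

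The cost is definition text and one CRF field. The CBC is already done at each treatment visit, and no scheduled procedure is added. The downside is that the reported relapse-free rate may be slightly lower.
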